12 STATISTICAL CONSIDERATIONS

12.1 Study Hypotheses

No formal statistical hypothesis testing will be performed in the primary safety analysis. The safety data will be summarized as described in Section [12.5.1](#).

The efficacy hypothesis to be tested is that the efficacy outcomes differ among the study arms at the later post-baseline study visits.

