12.5 Final Analysis Plan

12.5.1 Primary Safety Analysis

Safety data will be summarized for all subjects in the Safety Population. Adverse event and SAE reporting requirements are found in Section 9.

Safety for study treatment groups will be evaluated by the incidence, severity, and type of AEs, and by changes from baseline in subjects' oral examination findings, vital signs, and clinical laboratory test results. Concomitant medications taken during the trial will be summarized and listed.

The number and percentage of subjects who experience an AE, SAE, treatment-related AE, treatment-related SAE, and AE leading to discontinuation from the study will be summarized. All AEs will be coded by system organ class and preferred term according to the terminology of the Medical Dictionary for Regulatory Activities, and severity will be graded according to the National Cancer Institute's CTCAE, Version 4.0.

All AEs will be summarized by system organ class and preferred term and by maximum CTCAE severity grade. Summaries will also be presented by relationship to study treatment. For AE summaries, emphasis will be placed on the summary of treatment-emergent AEs, defined as new AEs reported after initiation of treatment or pre-existing conditions that worsen during the treatment period.

Subjects who withdraw from study treatment because of an AE will be listed.

The incidence of development or progression of periodontal disease at Day 28 will be reported for each study arm as part of the primary safety analysis. Development of disease or progression of existing periodontitis is defined as an increase from baseline of 2 mm or more in either the PD or CAL measures.

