8. SAFETY EVALUATION

8.1 Overview of Safety Analysis Methods

All safety analyses will be carried out using the Safety Population.

- Adverse events (AEs)
- Unanticipated problems
- Vital signs
- Laboratory determinations (hematology, serum chemistry, and urinalysis)
- Physical examinations
- Dental examinations

With the exception of the progression of periodontitis based on the dental examinations, no statistical comparisons between the treatment groups are planned for the safety variables.

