8.2 Progression of Periodontitis

Progression of periodontitis will be defined as an increase of 2 mm or more in pocket depth (PD) or clinical attachment level (CAL) from the Day 0 baseline measurement. The frequency (percent) of subjects with progression of periodontitis will be summarized by study arm, visit, and overall. Generalized linear mixed models regression based on a binomial distribution and logit link will compare the odds ratios of the overall incidence of the progression of periodontitis among the study arms at the Day 14 and Day 28 time points. The results of the generalized linear mixed model will be presented in a table and include p-values and odds ratios (with 95% CI) for the treatment arm comparisons at the two study visits. The p-values will not be adjusted for multiplicity.

The generalized linear mixed models analyses will automatically adjust for any missing values provided the missing values are missing at random; and thus, no additional imputation is necessary for missing values that are missing at random.

Missing observations are “not missing at random” if their missing-ness is possibly correlated with disease progression or efficacy. Missing PD or CAL observations due to missed visits or early study withdrawal will be deemed “not missing at random” if there were any treatment-emergent AE (TEAE) prior to or concurrent with a subject’s missed visit and the relationship between the TEAE and study drug was rated as “Possible”, “Probable”, or “Definite”.

If more than 5% of the PD or CAL measures are missing, or any missing PD or CAL measures are deemed “not missing are random”, then a sensitivity analysis will be performed by repeating the above generalized linear mixed model with all missing values imputed as having progression of periodontitis. The sensitivity analysis will also be triggered if for any other reason the principal investigator suspects that missing values may bias the analysis. The reasons a sensitivity analysis is triggered will be footnoted in the sensitivity analysis table.

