11. CHANGES TO THE ANALYSES PLANNED IN THE PROTOCOL

The safety and efficacy populations were expanded on to describe the handling of subjects that received the wrong treatment.

[figure not shown]

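### SAP 8.2 adds an undeclared between-arm test of periodontitis progression, using a model that gives no finite odds ratio for any contrast with an arm at 0% or 100% events

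*SAP*

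**What the plan says.** Protocol 3.2.1 makes development or progression of periodontitis part of the primary safety outcome. On testing, Protocol 12.1 says "No formal statistical hypothesis testing will be performed in the primary safety analysis". For this endpoint, Protocol 12.5.1 says "The incidence of development or progression of periodontal disease at Day 28 will be reported for each study arm", as part of that analysis.

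SAP 8.1 makes one exemption among the safety variables: "With the exception of the progression of periodontitis based on the dental examinations, no statistical comparisons between the treatment groups are planned". SAP 8.2 keeps a frequency summary by arm and visit and adds a model: "Generalized linear mixed models regression based on a binomial distribution and logit link will compare the odds ratios of the overall incidence". The output is to include "p-values and odds ratios (with 95% CI) for the treatment arm comparisons at the two study visits", and "The p-values will not be adjusted for multiplicity". The event is an "increase of 2 mm or more in pocket depth (PD) or clinical attachment level (CAL) from the Day 0 baseline measurement"; the number of sites that must meet it is not given.

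The only sensitivity analysis in SAP 8.2 refits the same model with every missing value counted as progression. SAP Section 11, which lists departures from the protocol, has one entry: "The safety and efficacy populations were expanded on to describe the handling of subjects that received the wrong treatment".

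**The concern.** Two things look wrong. First, the protocol and the SAP disagree on whether a primary safety endpoint is tested between arms, and the section meant to record such changes is silent on it.

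Second, a logit model fitted by maximum likelihood breaks down when an arm has no events, or only events, at a visit. The arms are small, and SAP 8.2 names no alternative, although SAP 9.3.2.1 and 9.3.3 do name fallbacks for the efficacy models.

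At stake is the between-arm table for the one safety endpoint that the SAP singles out for comparison. It could carry odds ratios and p-values that reflect only where the software stopped iterating. A replacement chosen after the blind is broken would be chosen with the data in view.

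**Working it through.** **Inputs.** Arm sizes are 50/50/25 enrolled and 40/40/20 after 20% attrition (SAP 2.5). Visits are Days 14 and 28 (SAP 8.2). Each subject has at least 20 teeth (Protocol 5.1) with 6 sites per tooth (Protocol 8.1.2), so at least 120 sites. The documents give no progression rate, so the rates below are assumptions.

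**The plan's own figures.** SAP Table 2.5.1 gives the chance of at least one event, 1 − (1 − p)^n. At p = 5%, 1 − 0.95^40 = 87.1% and 1 − 0.95^20 = 64.2% (64.15% unrounded), as stated. All 24 cells reproduce within 0.1 point. The complement is the chance of an arm with no events: 12.9% for n = 40 and 35.8% for n = 20.

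**Chance of an arm with no events at a visit.** With independent arms and a common rate, put q(n) = (1 − p)^n. For test or placebo the chance is 1 − (1 − q(n))². For any of the three arms it is 1 minus the product of the (1 − q) terms. Example at p = 5%, 50/50/25: q(50) = 0.077 and q(25) = 0.277. Test or placebo: 1 − 0.923² = 15%. Any arm: 1 − 0.923² × 0.723 = 38%.

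| Assumed rate | Test or placebo, 50/50 | Test or placebo, 40/40 | Any arm, 50/50/25 | Any arm, 40/40/20 |
|---|---|---|---|---|
| 3% | 39% | 50% | 67% | 77% |
| 5% | 15% | 24% | 38% | 51% |
| 10% | 1% | 3% | 8% | 15% |
| 15% | 0.1% | 0.3% | 2% | 4% |

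The same figures apply to an all-event arm at rates of 97%, 95%, 90% and 85%. The table cannot be narrowed from the documents. If one site is enough and sites are independent (both assumed), a per-site rate r gives 1 − (1 − r)^120 of subjects: 1.2% at r = 0.01%, 11% at 0.1%, 70% at 1% and 97% at 3%.

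**What the model does.** A random-intercept logistic model with arm-by-visit terms (implied by the by-visit output, not written out in the SAP) was fitted to invented counts:
- No events in the test arm at either visit: the test-placebo log odds ratios ran to about −25. The standard error was about 12,000, 0 or 17,000 depending on the convergence tolerance. Placebo against no-rinse stayed finite (odds ratios about 2.6 and 1.06).
- No events in the no-rinse arm only: test against placebo stayed finite (0.47 at Day 14, 0.25 at Day 28).
- No events in the test arm at Day 14 only: only the Day 14 contrasts with that arm failed.

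The random-effect SD reached its upper bound (3.32) in these fits, so the finite odds ratios are illustrative only. A plain logit fit of 0/40 against 4/40 shows the mechanism. After 5, 10, 20 and 35 iterations the log odds ratio was −4.4, −9.4, −19.4 and −34.4, and the Wald p-value rose from 0.09 to 0.76 and then to 1.00.

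**Methods that tolerate an arm with no events.** The exact two-sided 95% interval for 0/40 is 0 to 1 − 0.025^(1/40) = 8.8%. For 0/40 against 4/40, the Firth odds ratio is (0.5/40.5)/(4.5/36.5) = 0.10, with 95% CI 0.005 to 1.92. Fisher's exact p is 0.12. The Miettinen-Nurminen statistic at zero difference is 0.10/√(0.05 × 0.95 × (2/40) × 80/79) = 2.04, above 1.96, so that interval just excludes zero. Valid methods can differ near the boundary, so the choice has to be made in advance.

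**The case against.** The strongest reply is that the protocol's deliverable is untouched. A reader might infer that the SAP replaces the descriptive result, or that a primary safety outcome could be lost. Neither follows: SAP 8.2 keeps the per-arm frequencies, which survive separation, and the protocol promises no between-arm estimate. Nor is the comparison hidden, since SAP 8.1 announces it; only the Section 11 entry is missing.

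The any-arm probabilities are driven by the no-rinse arm, which SAP 2.5 describes as less important. The test-or-placebo columns are the ones that bear on the main contrast. All the rates are assumed, and the all-event extreme needs further assumptions about sites that the documents do not make.

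A reader might also infer a large familywise error from six unadjusted tests (three pairs at two visits). A calculation that treats them as independent does not fit: they share arms and subjects. In sparse data the Wald test is also far below its nominal level: at 50 per arm its type I error for test against placebo at one visit is 0.2% at a 5% rate and 2.4% at 10%, counting separated tables as non-significant. That a non-significant result would be read as evidence of safety is possible, but nothing in the SAP draws that inference.

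Finally, pairwise risk differences and Day 14 contrasts also go beyond Protocol 12.5.1, and a 95% interval can be read as a test. That stands, which is why any comparison kept should be labelled descriptive and declared. None of this answers the conflict with Protocol 12.1 or supplies a method for an arm at 0% or 100%.

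**Conclusion.** The point holds in two parts. The conflict between Protocol 12.1 and SAP 8.1-8.2, undeclared in SAP Section 11, rests on the text alone.

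The model failure is certain for any contrast with a 0% or 100% arm at a visit, given arm-by-visit terms and ordinary maximum likelihood. That is two of the three pairwise contrasts at the visit if one arm is affected. How likely it is depends on a rate that nobody has stated: material for test against placebo at about 5% or below (or 95% or above), small at 10%, and negligible in the middle of the range.

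The sensitivity analysis is no repair. With 20% attrition planned, its trigger of more than 5% missing is likely to be met. Where an arm has no observed events, its finite odds ratio would then rest wholly on imputed ones. The change should be made before database lock, but the descriptive safety result does not depend on it.

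**What to change.** In SAP 8.2:
- Keep the frequency summary and add an exact 95% CI for each arm at Days 14 and 28.
- Replace the mixed-model contrasts with pairwise risk differences at each visit, with exact or Miettinen-Nurminen 95% CIs. Name one method now. Present the differences as descriptive, without p-values, in line with Protocol 12.1.
- If an odds ratio is kept, estimate it by Firth-penalised logistic regression at each visit.
- Run the missing-counted-as-progression sensitivity analysis with the same method.

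In SAP Section 11, list the between-arm comparison and the added Day 14 time point as changes from Protocol 12.1 and 12.5.1.

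The cost is a rewrite of SAP 8.2, including its missing-data text, and the loss of the mixed model's repeated-measures and missing-at-random handling. Per-visit estimates use observed subjects only, so the missing-as-progression analysis carries more weight. No new data are needed.

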8.3 Extent of Exposure

Summary statistics will be presented for the treatment exposure. Treatment exposure will be defined as the number of days that the subject performed their allocated oral rinse treatment and the total volume of rinse used.

8.4 Adverse Events

All AEs will be coded to a system organ class (SOC) and preferred term (PT) using the most current version of the Medical Dictionary for Regulatory Activities (MedDRA). All tabular AE summaries will be for TEAEs. TEAEs will be defined as those AEs with an onset on or after the date of first dose of study drug (study visit 1: Day 0). If an AE was recorded prior to the first dose of study drug and there was an increase in its severity, the AE will be considered a TEAE. All other AEs will be classified as non-treatment-emergent. Treatment-emergent AEs will be flagged in all AE data listings.

An overall summary table will be developed to report the number of events and the incidence of participants having at least one event in the following categories:

- TEAEs
- TEAEs indicated as serious (SAEs)
- TEAEs that lead to study drug discontinuation
- TEAEs with an outcome of death
- TEAEs that were reported as having a definite/certain or possible relation to study drug
- TEAEs reported as having a severity rating of severe

In addition, a summary table of TEAEs classified by system organ class (SOC) and preferred term (PT) will be provided for each of the following:

- TEAEs
- TEAEs by maximum severity
- TEAEs by relationship to study drug

The summary of all TEAEs will present both the number of TEAEs and the incidence of TEAEs. The summary of TEAEs by severity, relationship to study drug, and week of treatment will only report the incidence of TEAEs. When reporting the number of TEAEs, if the same TEAE occurs for a subject on multiple occasions the event will be counted once for each occurrence. When reporting the incidence, a subject will only be counted once if they ever experience an event within the SOC and ever experience the individual PT.

For the summary of TEAEs by severity, if the severity of the TEAE is not reported, then the severity of the TEAE will be counted as severe. If the same TEAE occurs for a subject on multiple occasions, the TEAE will be categorized according to the highest severity rating for that TEAE in that subject. For the summary of TEAEs by relationship to study drug, if the relationship is missing, it will be counted as definite/certain. If the same TEAE occurs for a subject on multiple occasions, the TEAE will be categorized according to the closest relationship to study drug reported for that TEAE in that subject.

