6.6 Concomitant Medications/Treatments

Subjects will receive instructions to avoid, during the 28 days of product use, any medications and dental procedures that could affect periodontal status (see exclusion criteria). At each study visit, subjects will be asked to report all concomitant medications and any dental care received or procedures performed during the study period.

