9 ASSESSMENT OF SAFETY

9.1 Specification of Safety Parameters

Parameters used to assess safety will include AEs spontaneously reported by the subject or observed by the investigator, solicited AEs captured by review of the memory aid while interviewing the subject, clinical laboratory values (reviewed by the on-site medical monitor), oral cavity examination, vital signs, and increases in pathogenic bacterial flora identified in plaque samples. All AEs will be coded by system organ class and preferred term according to the terminology of the Medical Dictionary for Regulatory Activities.

Monitoring of AEs will be conducted throughout the study. New AEs, including SAEs, will be captured through the final study visit. In addition, all AEs will be captured at the final telephone follow-up conducted 2 months after the last use of study product. Adverse events will be followed in accordance with Good Clinical Practice. Serious adverse events will be immediately reported to the IND sponsor, to NIDCR, and to the IRB within 24 hours of becoming aware of the event, and will be monitored until they are resolved or are clearly determined to be due to a subject's stable or chronic condition or intercurrent illness(es). Unanticipated problems (UPs) will also be captured and reported to the IRB and FDA as required by regulation.

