2.2 Overall Study Design and Plan

This study has a randomized parallel placebo-controlled double-blind study design with one treatment arm and two control arms (placebo oral rinse, and no rinse controls). Subjects in the treatment (N=50) and placebo rinse (N=50) arms will be double-blinded and receive oral rinse (BLXA4-ME or placebo rinse) to be applied once daily after morning teeth brushing. The no-rinse control arm (N=25) will be blinded from the investigators and apply no oral rinse. Subjects will perform their randomized treatment for 28 days. Safety parameters will be assessed before treatment and at Days 3, 7, 14, 21, and 28 after the initial treatment. Efficacy parameters will be assessed before treatment and Day 14 and Day 28 after the initial treatment. Total duration of subject participation will be 3 months (in clinic visits through 28 days, and a follow-up safety phone call at 2 months after last product use).

The Study Flow Chart and the Schedule of Events can be found in Appendices 13.1 and 13.2, respectively.

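### SAP 8.4 gives treatment-emergent AEs no end date, so the descriptive AE tables for a 28-day exposure pool on-product events with about 62 days of off-product follow-up

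*SAP*

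**What the plan says.** SAP 8.4 fixes the start of the treatment-emergent period: "TEAEs will be defined as those AEs with an onset on or after the date of first dose of study drug", with Day 0 given as that date. It states no end. An AE recorded before first dose also counts if its severity later increases, again with no time limit. The same section says: "All tabular AE summaries will be for TEAEs".

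On exposure and follow-up, SAP 2.2 says: "Subjects will perform their randomized treatment for 28 days". It then describes "a follow-up safety phone call at 2 months after last product use". Protocol 9.1 confirms that "all AEs will be captured at the final telephone follow-up conducted 2 months after the last use of study product". The schedules of events in both documents place this call at Day 90 ± 14 days.

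Protocol 12.5.1 defines treatment-emergent events as "new AEs reported after initiation of treatment or pre-existing conditions that worsen during the treatment period". New events are therefore open-ended in the protocol too, but worsening is confined to the treatment period. SAP 11, which records changes from the protocol, mentions only the handling of subjects who received the wrong treatment.

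SAP 8.4 refers once to an incidence summary by week of treatment. That summary is in neither bulleted list of tables in the section, and its weeks are not defined. SAP 12 leaves the full list of tables to a separate document.

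**The concern.** The primary objective is the safety of 28 days of daily rinsing, and descriptive AE incidence by arm is a main part of the primary analysis. If the rinse causes events only while it is in use, off-product events arrive at background rate in every arm. They raise every arm's cumulative incidence and narrow the visible gap between arms.

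The two periods also differ in how events are found. On product there are visits on Days 3, 7, 14, 21 and 28, with oral examination and memory-aid review; off product there is one telephone call. The restriction on dental care is tied to product use: "Subjects will receive instructions to avoid, during the 28 days of product use, any medications and dental procedures that could affect periodontal status". Protocol 2.5.1 tells subjects that they may need periodontal treatment later. Oral events after such care could fall under the same preferred terms as rinse irritancy, although the documents do not show how often.

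**Working it through.** **The plan's own figure.** The AE sample-size table uses P(at least one event) = 1 − (1 − p)^n. For n = 40 and p = 4%, 1 − 0.96^40 = 80.5%, as stated. All 24 cells reproduce. The formula contains no time window, so the table does not settle this point.

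**Share of follow-up time off product** = (T − 28)/T, with T the day of the call.
- T = 90: 62/90 = 68.9%
- T = 76: 48/76 = 63.2%
- T = 104: 76/104 = 73.1%

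**Share of events off product.** The documents give no event rates. Assume a constant background hazard, an on-product hazard multiplied by k in the active arm (1 on placebo), and a fraction c of off-product events captured by the call. The share is 62c/(28k + 62c).
- Placebo: 62/90 = 69% at c = 1; 15.5/43.5 = 36% at c = 0.25.
- Active: 62/118 = 53% at k = 2, c = 1; 15.5/99.5 = 16% at k = 3, c = 0.25.

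The 69% share of days therefore equals the share of events only with a constant rate, full capture and no drug effect.

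**Dilution of a 10-point excess.** Let b be the assumed background risk per 28 days and d = 0.10 the on-product excess, with background hazard only after Day 28.
- Control by Day 90: 1 − (1 − b)(1 − b)^(62c/28)
- Active by Day 90: 1 − (1 − b − d)(1 − b)^(62c/28)
- Difference: d(1 − b)^(62c/28)

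Differences below are taken before rounding.

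| b | Day 90 control vs active, c = 1 | Difference, c = 1 | Difference, c = 0.25 |
|---|---|---|---|
| 2% | 6.3% vs 15.8% | 9.6 points | 9.9 points |
| 5% | 15.2% vs 24.1% | 8.9 points | 9.7 points |
| 10% | 28.7% vs 36.6% | 7.9 points | 9.4 points |
| 20% | 51.2% vs 57.3% | 6.1 points | 8.8 points |
| 30% | 68.2% vs 72.8% | 4.5 points | 8.2 points |

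**Ratio scale.** With b = 10% and the on-product hazard doubled, the 28-day risks are 10.0% vs 19.0% (ratio 1.90). By Day 90 with full capture they are 28.7% vs 35.9% (ratio 1.25). With 25% capture the ratio is 1.56. Ratios shrink more than differences when background is low.

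**The worsening rule.** Protocol 12.5.1 counts worsening only within the treatment period; SAP 8.4 sets no limit. Protocol 9.1.1 treats conditions present at screening as baseline, so few AEs will be recorded before first dose and then worsen. It also has deterioration at any time in the study recorded as an AE. If the recorded onset is the date of deterioration, the SAP's start-date rule counts it up to Day 90, whereas the protocol's rule would not count it after treatment ends.

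**The case against.** Several points on the other side stand.

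- Following subjects after the last rinse is a deliberate safety feature in a first-in-human study, and the open end for new AEs comes from the protocol. The remedy must not drop late events.
- Protocol 12.1 plans no hypothesis test in the primary safety analysis, and SAP 8.1 plans no between-arm safety comparison except for periodontitis progression. A reader might infer a loss of power, but there is no planned AE test to lose it.
- A reader might infer that 69% of events are off product. That figure is a share of days, and one call may capture fewer events than five visits.
- A reader might infer that the whole safety evaluation is diluted. Scheduled oral and OMAS examinations, laboratory tests, plaque flora and periodontal measurements all end at Day 28, so those summaries are not.
- For specific preferred terms, where irritancy would show, background is likely to be lower than for an any-AE row. The plan's own discussion highlights specific AEs at 4% to 8%. The absolute dilution is then small.
- The relationship table offers some separation, because an established alternative cause is a criterion for unrelated under Protocol 9.3.1. Contamination by later dental care is possible but not demonstrated.

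The week-of-treatment phrase is a weaker defence. It suggests that a time split was intended, but it defines neither the weeks nor an end of treatment. The separate table list may contain such a table; SAP 8.4 as written does not secure it.

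**Conclusion.** The point holds for the descriptive AE tables. As written, SAP 8.4 pools 28 on-product days with about 62 off-product days that are observed differently. The direction of dilution is clear if any excess is confined to product use. Its size rests on assumed background risks, a constant background hazard and an assumed capture rate: a 10-point excess becomes 9.6 to 4.5 points with full telephone capture, and 9.9 to 8.2 points with 25% capture. The documents support neither a claim about the share of events nor a claim that a planned inference is weakened.

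The mismatch on worsening conditions depends on no assumed rate. It is a departure from Protocol 12.5.1 that SAP 11 does not list. Together these are a worthwhile, low-cost improvement to the AE part of the primary analysis, not a flaw that undermines the trial.

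**What to change.** In SAP 8.4, present the TEAE tables (overall, SOC/PT, severity, relationship) in three columns per arm:
- on-treatment: onset from Day 0 through the Day 28 or withdrawal visit, by the same rule in all three arms, with any short lag stated in advance;
- post-treatment: onset after that, up to the Day 90 call;
- combined.

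Read the 28-day safety question from the on-treatment column alongside the combined one. A visit-based cut-off works for the no-rinse arm and does not need a last-use date, which the documents do not clearly say is recorded. Because Protocol 7.7 allows telephone contact in place of a withdrawal visit, state which date then applies.

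Define the week-of-treatment summary and list it among the tables, or remove it. Either restore the protocol's limit on worsening of pre-existing conditions or list the change in SAP 11.

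The cost is SAP wording and extra columns. AE onset is already collected (Protocol 9.1.1), and the SAP is being written before database lock. The downside is longer tables and a cut-off that has to be chosen; no event is lost.

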9.3.1 Relationship to Study Intervention

The clinician's assessment of an AE's relationship to test article is part of the documentation process, but it is not a factor in determining what is or is not reported in the study. If there is any doubt as to whether a clinical observation is an AE, the event should be reported. All AEs must have their relationship to study product assessed using the following terms:

- Related (possible, probable, definite) events meet 1 or more of the following criteria:
 - The event is known to occur with the study intervention.
 - There is a temporal relationship between the intervention and event onset.
 - The event abates when the intervention is discontinued.
 - The event reappears upon a rechallenge with the intervention.
- Not related (unlikely, not related) events meet 1 of the following criteria:
 - There is no temporal relationship between the intervention and event onset.
 - An alternate etiology has been established.

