9.5 Rules for Study Suspension or Discontinuation

The NIDCR medical monitor will review all SAEs and UPs in an expedited fashion. In the event of unacceptable toxicity, the trial will be stopped prematurely to prevent harm to subjects. In addition, any injuries, SAEs, or other unexpected AEs involving risk to subjects or others, and occurring at a frequency above that considered acceptable by the investigators, IND sponsor, NIDCR, or IRB, may result in a temporary or permanent halt to the study. The study may be suspended for a safety review and consideration of study discontinuation if:

- One or more subjects experiences a clinically significant event or laboratory abnormality determined to be Grade 3 or higher and related (possibly, probably, definitely) to use of the investigational product;
- Two or more subjects experience a similar event determined to be Grade 2 or higher and related (possibly, probably, definitely) to use of the investigational product;
- One or more subjects experiences a Grade 2 or higher event that does not resolve within 14 days.

The NIDCR medical monitor or DSMB may request to be unblinded to the entire study when evaluating whether to suspend or discontinue the study. In the event of study unblinding, a non-study statistician will be assigned as the “unblinded statistician” to assist in unblinding and any safety review.

Any proposed changes in the consent form or research procedures resulting from any safety findings are to be submitted by the principal investigator to the IRB for approval.

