8.5 Deaths, Serious Adverse Events, and Other Significant Adverse Events

In addition to these summary tables, the incidence of adverse events leading to death, the incidence of SAEs, and incidence of TEAEs that led to study drug being discontinued will be presented in summary tables and listings. The summary listings will provide all of the information reported for that AE and will include the number of days from date of first dose to date of the occurrence of the AE.

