12. LIST OF PLANNED TABLES, FIGURES, AND LISTINGS

[figure not shown]
Lists of planned tables, figures, and listings will be provided in a separate document.

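### The headline treatment-related row in SAP 8.4 leaves out events rated probable, and no table described in SAP 8.4 or 8.5 gives the treatment-related SAE count that Protocol 12.5.1 requires

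*SAP*

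**What the plan says.** **How related is defined.** Protocol 9.3.1 sets the scale: "Related (possible, probable, definite) events meet 1 or more of the following criteria". The suspension rules in Protocol 9.5 use the same three levels for an event "determined to be Grade 3 or higher and related (possibly, probably, definitely) to use of the investigational product". The SAP uses them too: SAP 8.2 decides whether missing data are informative by asking whether the event was "rated as “Possible”, “Probable”, or “Definite", and SAP 9.1.1 repeats that rule for the efficacy data.

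**What the safety tables report.** Protocol 12.5.1 promises the "number and percentage of subjects who experience an AE, SAE, treatment-related AE, treatment-related SAE", and also AEs leading to discontinuation from the study. To deliver this, the overall table in SAP 8.4 gives events and subjects in six categories. The related category is "TEAEs that were reported as having a definite/certain or possible relation to study drug". SAP 8.4 adds three tables by system organ class (SOC) and preferred term (PT): all TEAEs, by maximum severity, and by relationship. For incidence in these tables, "a subject will only be counted once if they ever experience an event within the SOC and ever experience the individual PT". SAP 8.5 adds tables and listings for "the incidence of adverse events leading to death, the incidence of SAEs, and incidence of TEAEs that led to study drug being discontinued".

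**What is left to another document.** SAP 12 says: "Lists of planned tables, figures, and listings will be provided in a separate document". SAP 11 declares one change from the protocol's analyses, the handling of subjects who received the wrong treatment. It mentions no change to the adverse event summaries.

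**The concern.** The related row names the strongest and the weakest related levels and skips the one between them. No reason is given, and none is apparent. A programmer working from SAP 8.4 alone would leave probable events out of the one table meant to give the overall treatment-related figure. The error can go only one way: the reported count can be too low, never too high.

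Separately, the protocol promises a count of subjects with a treatment-related SAE, and the tables described in the SAP do not produce it.

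Both figures belong to the primary objective. Protocol 12.1 plans no formal hypothesis test for the primary safety analysis, and Protocol 9.3.2 says this is the first use of the rinse in humans. Descriptive counts such as these therefore carry most of the safety message.

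**Working it through.** The plan states no figure to reproduce. The check sets the texts side by side and then works out the effect per subject.

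**Step 1. Levels counted as related**

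| Place | Levels named | Number |
|---|---|---|
| Protocol 9.3.1 | possible, probable, definite | 3 |
| Protocol 9.5 | possible, probable, definite | 3 |
| SAP 8.2 | possible, probable, definite | 3 |
| SAP 9.1.1 | possible, probable, definite | 3 |
| SAP 8.4, overall table | definite/certain, possible | 2 |

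Only the SAP 8.4 row omits probable.

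**Step 2. Consequence of following the row literally.** The overall table reports both events and subjects.
- Event count: every probable event is lost, even where the same subject has another related event.
- Subject count: a subject is lost only if all of that subject's related TEAEs are rated probable.

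**Step 3. Can another table restore the subject count?** The SOC/PT table by relationship should show the probable events. But it counts a subject once in each SOC and once in each PT, and no line totalling over all SOCs is described. A subject with related events in two SOCs appears in both, so adding the rows gives 2 for 1 subject. The rows therefore cannot simply be summed to give the number of subjects with any related TEAE.

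**Step 4. Effect per affected subject.** The row falls by 1/N for each such subject, where N is the arm's Safety Population.
- N = 50, the planned enrolment of a rinse arm: 1/50 = 2.0 percentage points.
- Under Protocol 5.5.2, subjects who withdraw before Day 14 are replaced. Under Protocol 12.2.1 they stay in the Safety Population if they were randomized and completed Baseline. Assume that all of the planned 20% attrition falls before Day 14 and that each subject is replaced once. Then N = 50 + 0.20 × 50 = 60, and 1/60 = 1.7 points.

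The documents give no basis for predicting how many subjects would be affected. The minimum is 0.

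**Step 5. Protocol 12.5.1 against the tables described in SAP 8.4 and 8.5**

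| Protocol 12.5.1 asks for subjects with | Described in the SAP |
|---|---|
| AE | Yes, as TEAEs (8.4) |
| SAE | Yes (8.4 and 8.5) |
| Treatment-related AE | Yes, but the row omits probable (8.4) |
| Treatment-related SAE | No table |
| AE leading to discontinuation from the study | Yes, worded as study drug discontinuation (8.4 and 8.5) |

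In the 8.4 overall table, seriousness and relationship are separate rows. The 8.4 SOC/PT tables are not split by seriousness, and nothing in 8.5 describes a split by relationship. From what is described, related SAEs could be found only one by one in the 8.5 listings.

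**The case against.** The best reply is that this is an editorial slip which the documents themselves resolve. The protocol fixes the meaning of related, the SAP uses the full scale twice elsewhere, and counting both ends of a scale without its middle makes no analytic sense. An informed programmer would read the row as the ends of a range. No data are lost either: the by-relationship table covers all TEAEs, the listings carry every event, and a total line is the kind of detail settled in a table shell.

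On the second part, the SAP's silence does not withdraw the protocol's requirement, and the separate table list may contain the missing table. A related SAE would hardly go unnoticed, because Protocol 9.5 provides expedited review of every SAE. If there are no SAEs, the missing count is zero.

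Much of this stands. The omission is probably unintended, its effect may be nil, and subject protection does not depend on these rows. The point about the separate list also stands: the second part is nearer to missing detail than to contradiction.

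Two things do not follow. The row does not read as a range; it names two levels. And data that can be recovered from listings are not the number and percentage that Protocol 12.5.1 promises. SAP 1 gives setting out the summary tables as one of the document's purposes, so a summary the protocol requires belongs in its text.

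**Conclusion.** Both parts hold.

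The related row in SAP 8.4 is wrong as written. It conflicts with the protocol's definition and with the SAP's own usage, and followed literally it can understate a primary safety figure. The understatement is 2.0 percentage points for each affected subject when N = 50, or 1.7 points under the N = 60 replacement assumption. The number of affected subjects cannot be determined and may be zero.

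The treatment-related SAE count is absent from every table described in SAP 8.4 and 8.5. That conclusion is limited to those sections, because the separate table list was not available for this review.

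This is a reporting error. It should be corrected, but no test, sample size or suspension rule rests on it.

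**What to change.** In SAP 8.4:

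1. Reword the related row to: *TEAEs with a possible, probable or definite relationship to study drug*.
2. Add a row for treatment-related SAEs, giving the number and percentage of subjects and using the same definition of related. Check that the separate table list agrees.

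Two optional clarifications: use the protocol's term *definite* in place of *definite/certain*, and state that the rule for missing relationship (counted as definite/certain), now given only for the by-relationship summary, also applies to the overall row.

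The cost is two lines of SAP text and the matching table-shell edits before database lock. No new data are needed. The only downside is that the reported counts may be higher.
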